- A common standard deviation of 0.3 L in each of the two groups is assumed, which is a consensus value based on the review of historical data from COPD trials.
- A difference of 0.12 L between the treatment group and the placebo group.
- A 2-sided t-test with 5% significance level.
- Fifteen percent (15%) of patients with missing data at Week 24 due to discontinuation or other reasons.
- Patients are randomized to the treatment group and the placebo group with a 1:1 ratio.

With these assumptions and 170 patients per group (340 patients in total), we will have 92.6% power to detect the difference of 0.12 L between the treatment group and the placebo group. The least significant difference between groups will be 0.07 L.

Randomization will be stratified by Screening/Visit 1 eosinophil count (see below) and by country.

To ensure scientific validity, alerts will be built into the interactive voice/web response system (IVRS/IWRS) to control the number of patients enrolled into each stratification groups, as follows:

1. Eosinophil <250 /mm³: approximately 50% (170) patients
2. Eosinophil ≥250 /mm³: approximately 50% (170) patients.

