Subgroup analyses of the average change from baseline to Week 16-24 in pre-BD FEV1 will be conducted in the same subgroups as for the primary endpoint based on the primary MMRM model for pre-BD FEV1 described above. Within each subgroup, descriptive statistics including number of patients, mean, SD, and LS means will be provided for each treatment group. Difference in LS means and the corresponding two-sided 95% CI will be provided for the comparison of

SAR440340 and placebo within each subgroup. Treatment-by-subgroup interaction and its p-value will be derived from a MMRM model. The model covariates will include sex, baseline height, smoking history (current vs. former smoker), baseline FEV1 value, treatment group, visit, treatment-by-visit interaction, baseline FEV1-by-visit interaction, the baseline eosinophil strata, region, subgroup (if different from the aforementioned covariates), subgroup-by-treatment interaction, and subgroup-by-treatment-by visit interaction.

2.4.4.2.2 *Change from baseline to Week 24 in post-bronchodilator FEV1*

The analysis method for this endpoint is identical to the analysis of the key secondary efficacy endpoint, the average change from baseline to Week 16-24 in pre-BD FEV1, except that here we only have the value at Week 24, not at Weeks 16 and 20. Similar analysis will be performed for the secondary efficacy population (high EOS group), without the baseline eosinophil strata in the model.

2.4.4.2.3 *Time to first moderate or severe AECOPD*

Time to first moderate or severe AECOPD that occurs from randomization up to week 52 will be analyzed using a Cox regression model with treatment, baseline eosinophil strata and region (pooled countries), number of severe COPD exacerbations experienced in previous year (0 vs. 1+) at baseline, smoking history (current vs. former smoker) and post-BD FEV1 percent predicted (<50% vs. ≥50%) at baseline as covariates. The hazard ratio (HR) between SAR440340 and placebo along with its 95% confidence interval will be estimated by the Cox model. The Kaplan-Meier (K-M) method will be used to estimate the probabilities of first AECOPD at specific time points for each group. P-value from the log-rank test stratified by baseline eosinophil strata and region will be provided.

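### The FEV1 subgroup interaction p-value has no stated contrast; on the natural reading it averages all model visits, not Weeks 16, 20 and 24

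*SAP*

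**What the plan says.** SAP 2.4.4.2.1, under its subgroup heading, sets the endpoint: "Subgroup analyses of the average change from baseline to Week 16-24 in pre-BD FEV1 will be conducted in the same subgroups". The subgroups meant are those already listed for the exacerbation rate. LS mean differences with 95% confidence intervals are given within each subgroup. On the test across subgroups it says "Treatment-by-subgroup interaction and its p-value will be derived from a MMRM model". The covariate list for that model ends with "subgroup-by-treatment interaction, and subgroup-by-treatment-by visit interaction". It gives no contrast, visit weighting or code for the interaction.

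The main treatment comparison in the same section is handled differently. Its sample code has an explicit LSMESTIMATE that puts one third on each of the last three visits and zero on the earlier ones.

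The visits in the main model are not written out. SAP Table 6 shows seven post-baseline pre-bronchodilator visits up to Week 24 (Weeks 2, 4, 8, 12, 16, 20, 24), whereas the LSMESTIMATE has five visit positions per arm. The Week 52 model is described as an additional analysis, so the main model is read here as ending at Week 24.

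**The concern.** When a model holds a treatment-by-subgroup term and the same term crossed with visit, the usual (Type III) test of the two-way term is an average over visits. It does not follow the endpoint. A programmer who takes the SAP at its word and reports the p-value printed for treatment-by-subgroup would place a test of the all-visit average beside estimates for Weeks 16-24.

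The two can part in either direction. A subgroup difference that builds up over time is diluted by early visits. One that is present early and gone by Week 16 may be declared although the endpoint shows none. Protocol Table 1 names eosinophil level, ICS use, fibrinogen and smoking status as subpopulations for FEV1, and in a proof-of-concept trial such results can inform the choice of population for later work.

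**Working it through.** **1. The plan's own FEV1 figure.** No power is stated for any interaction; the only FEV1 design figure is the overall power in Protocol 9.2. Inputs there: for the spread, "A common standard deviation of 0.3 L in each of the two groups is assumed"; for the effect, 0.12 L between arms; the test is two-sided at 5%; for losses, "Fifteen percent (15%) of patients with missing data at Week 24 due to discontinuation or other reasons"; and 170 per arm, allocated 1:1.
- Evaluable per arm: 170 × 0.85 = 144.5.
- SE = 0.3 × √(2/144.5) = 0.0353 L.
- Power = Φ(0.12/0.0353 − 1.96) = 92.5% (noncentral t: 92.3%). Stated: 92.6%.
- Least significant difference: about 0.07 L, as stated.

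The inputs reproduce.

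**2. What the two-way test estimates.** The Type III estimable function for treatment-by-subgroup was built for a two-level subgroup, in a model with treatment, visit, treatment-by-visit, subgroup, treatment-by-subgroup and the three-way term. It has 1 df and equal weight on every visit. Adding subgroup-by-visit, which the SAP does not list, leaves these weights unchanged.

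| Test | Weight per visit | Weight before Week 16 |
|---|---|---|
| Two-way term, 7 visits | 1/7 | 4/7 = 57% |
| Two-way term, 5 visits | 1/5 | 2/5 = 40% |
| Week 16-24 contrast | 1/3 on Weeks 16, 20, 24 | 0 |

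**3. Loss under one assumed build-up.** No document gives an onset curve or a within-patient correlation, so both are assumptions. Let the subgroup difference reach 0, 25, 50, 75, 100, 100, 100% of its final size over the seven visits.
- Tested quantity: (0 + 0.25 + 0.5 + 0.75 + 1 + 1 + 1)/7 = 4.5/7 = 0.643 of the target.
- Variance factor w′Rw: compound symmetry 0.7 gives 0.743 (all visits) and 0.800 (Weeks 16-24); AR(1) 0.85 gives 0.714 and 0.872.
- z ratio: 0.643 × √(0.800/0.743) = 0.667, and 0.643 × √(0.872/0.714) = 0.710.
- Power of a test that would otherwise have 80%: Φ(2.80 × ratio − 1.96) = 46% and 51%.

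With five visits taken as Weeks 8, 12, 16, 20 and 24, the profile is 50, 75, 100, 100, 100%. The tested quantity is 4.25/5 = 0.85, the z ratio 0.87-0.90 and the power 69-71%. Other choices of the two early visits give less, down to 46%.

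**4. Constant difference.** Both tests then target the same value. With seven visits the z ratio is √(0.800/0.743) = 1.04 to √(0.872/0.714) = 1.10, in favour of the all-visit test.

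**5. The opposite error.** Assume two equal subgroups, 289 evaluable patients (2 × 144.5), SD 0.3 L, compound symmetry 0.7, seven visits, and a 0.24 L subgroup difference through Week 12 that is zero from Week 16.
- All-visit estimate: 0.24 × 4/7 = 0.137 L.
- SE = √(0.09 × 0.743 × 16/289) = 0.061 L.
- The all-visit test rejects 62% of the time; the Week 16-24 contrast rejects 5%.

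Over correlations of 0.5 to 0.85, compound symmetry or AR(1), the 62% ranges from 55% to 91%.

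**The case against.** A reader might infer that the SAP prescribes an all-visit test. It does not: it names neither a Type III test nor the two-way term as the source of the p-value. The paragraph opens with the Week 16-24 endpoint and rests on the primary model, whose inference comes from a Week 16-24 LSMESTIMATE. The three-way term is also what makes a Week 16-24 interaction contrast estimable. This stands: the defect is an unspecified test whose default misses the endpoint. Even so, two programmers could report different p-values from the same text.

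A reader might also take seven visits and a fall to about half power as established. The seven visits come from the schedule; the sample code has five positions, and which early visits they stand for is not stated. The loss depends on an assumed onset profile. The 80% starting point is also generous. Under the assumptions of step 5, the Week 16-24 contrast has SE √(0.09 × 0.800 × 16/289) = 0.063 L, so 80% power needs a subgroup difference of about 2.80 × 0.063 = 0.18 L, above the 0.12 L planned for the whole trial.

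The stakes are bounded too. The subgroup objectives sit under the tertiary/exploratory heading of Protocol Table 1, where the FEV1 endpoint is the change to Week 24. Within-subgroup Week 16-24 estimates with confidence intervals are reported regardless, and high-eosinophil patients have their own efficacy population. SAP 2.4.4.4 makes all p-values nominal. These points limit the consequence but do not supply the missing contrast.

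**Conclusion.** The point holds as a gap in specification with a misleading default. If the p-value is the test of the two-way term, 57% (seven visits) or 40% (five visits) of its weight falls before Week 16; that follows from the model terms and needs no clinical assumption. The practical effect does need assumptions. Under the build-up above, 80% power becomes about 46-51% with seven visits, or about 69-71% with five visits taken as Weeks 8-24. An early, vanished difference could be flagged falsely. With a constant difference nothing is lost.

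The documents do not support saying that the SAP mandates the wrong test, or that any error rate is compromised. What is affected is how subgroup consistency for the key secondary endpoint will be read. The change should be made, but the trial's main results do not depend on it.

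**What to change.** In the subgroup part of SAP 2.4.4.2.1, define the FEV1 interaction p-value as the contrast, from the same MMRM, between subgroup levels of the treatment difference averaged over Weeks 16, 20 and 24. Use an LSMESTIMATE on treatment*subgroup*visit, with a joint F test for subgroups of more than two levels, such as region, ICS dose level, weight and BMI. List the visits in the model, so that the seven scheduled visits and the five positions in the sample code are reconciled.

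The cost is one or two sentences and one code statement per subgroup; no new data are needed. The downside is slightly less power if effect modification is constant from the first visit.

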2.4.4.2 Analyses of secondary efficacy endpoints

2.4.4.2.1 Average change from baseline to Week 16-24 in pre-bronchodilator FEV1

Main statistical model and adjustment of covariates

The key secondary efficacy endpoint, the average change from baseline to Week 16-24 in the pre-bronchodilator FEV1 will be analyzed using a mixed-effect model with repeated measures (MMRM) approach. Model-based average across Weeks 16, 20 and 24 will be compared between the treatment groups. The dependent variable is the change from baseline in pre-bronchodilator FEV1 at each time point. The model will include sex, baseline height, smoking history (current vs. former smoker), baseline FEV1 value, treatment group, visit and treatment-by-visit interaction, baseline FEV1-by-visit interaction, the baseline eosinophil strata, and region (pooled countries) as covariates. An unstructured correlation matrix will be used to model the within-patient correlations. Parameters will be estimated using restricted maximum likelihood method with the Newton-Raphson algorithm. No imputation will be performed on missing FEV1 measurements.

Descriptive statistics including number of patients, mean, standard error, and least squares (LS) means will be provided for each treatment group. Difference in LS means and the corresponding two-sided 95% CI and p-value will be provided for the comparison. Sample SAS code can be found below:

```
proc mixed data=fevldata method=reml;
  class usubjid sex csmoker trt01pn cntygr1 eosbgpln avisitn;
  model chg = sex height csmoker trt01pn trt01pn *avisitn FEV1bl
  FEV1bl* avisitn cntygr1 eosbgpln avisitn
           trt01pn*avisitn /ddfm=kr residual;
  repeated avisitn / subject=usubjid type=un;
  lsmestimate trt01pn*avisitn 'Tx wks 16-24 avg minus pbo wks 16-24 avg' 0 0
1 1 1 0 0 -1 -1 -1/ divisor=3;
  lsmeans trt01pn*avisitn / pdiff cl e;
  ods output LSMeans=LSMeans Diffs=Diffs LSMEstimates=LSMEstimates;
run;
```

If the above model fails to converge, the specification may be changed as follows: 1) use maximum likelihood estimation instead of restricted maximum likelihood method; 2) specify a different covariance structure to reduce the number of unknown parameters to be estimated, the path will be UN→TOEPH→TOEP→AR(1).

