Time to first moderate or severe AECOPD is defined as (onset date of the first moderate or severe AECOPD-randomization date+1). If the patient did not experience any moderate to severe AECOPD events, the event time will be considered as censored at date of EOT or the last contact date within the planned treatment duration. Below is sample SAS code for the Cox regression model:

```
proc phreg data=ttevent;  
class trt01pn eosbgpln cntygr1 nscopd csmoker ppredFev1/ param = glm;  
model aval*cnsr(1) = trt01pn eosbgpln cntygr1 nscopd csmoker ppredFev1;  
estimate "SAR440340 vs Placebo"          trt01pn -1 1 / exp;  
ods output Estimates = Estimates;  
  
run;
```

Similar analysis will be performed for the secondary efficacy population (high EOS group), without the baseline eosinophil strata in the model.

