rrU = exp(uclmean);  
run;
```

5. For control-based PMM-MI, we will replace the following command in Step 2 under “**data** ckrepimp”

```
lin=Intercept+mtx*txval+mst1*st1val+mreg1*reg1val+mreg2*reg2val+mx*xval;  
by
```

```
lin=Intercept+0*txval+mst1*st1val+mreg1*reg1val+mreg2*reg2val+mx*xval;
```

This way, we will use the control rate to impute the missing data.

6. For tipping-point analysis, we will replace the following command in Step 2 under “**data** ckrepimp”

```
lin=Intercept+mtx*txval+mst1*st1val+mreg1*reg1val+mreg2*reg2val+mx*xval;  
by
```

```
lin=Intercept+(mtx+delta)*txval+mst1*st1val+mreg1*reg1val+mreg2*reg2val+mx*xval;
```

where “delta” is a sequence of positive numbers representing the diminishing treatment effect for patients in the treatment group needing imputation. A table of p-values for the treatment effect in the analysis model with the imputed data and the “delta” value will be provided.

Change from baseline in FEV1

Pattern mixture model by multiple imputation

1. Partially impute data using Markov Chain Monte Carlo (MCMC) method to obtain 40 datasets with monotone missing pattern:

```
proc mi data=&DSTIN seed=&seed nimpute=40 out=monotone;  
  mcmc impute=monotone;  
  var base &chg_all;  
run;
```

where &chg_all includes change from baseline in FEV1 at all visits.

2. For each of the imputed dataset with monotone missing pattern, the remaining missing data will be imputed by a regression model

```
proc mi data=monotone seed=&seed nimpute=1 out=data_imp;
  by _imputation_;
  class trt01pn sex eosbgp1n cntygr1 endtrs1;
  var sex hgtbl eosbgp1n cntygr1 trt01pn endtrs1 base
      &chg_all;
  monotone reg;
run;
```

3. Analyze the 40 imputed datasets by the ANCOVA model described in [Section 2.4.4.2](#):

```
proc mixed data=data_imp method=reml;
  by _imputation_;
  class usubjid trt01pn sex cntygr1 eosbgp1n avisitn;
  model chg12 = trt01pn sex hgtbl cntygr1 eosbgp1n avisitn
      trt01pn*avisitn base base*avisitn /ddfm=kr residual;
  repeated avisitn / subject=usubjid type=un;
  lsmestimate trt01pn*avisitn 'Tx wks 16-24 avg minus pbo wks 16-24 avg' 0 0
1 1 1 0 0 -1 -1 -1 / divisor=3;
  lsmeans trt01pn*avisitn / pdiff cl e;
  ods output LSMeans=LSMeans_imp Diff=Diff_imp
LSMEstimates=LSMEstimates_imp;
run;
```

4. Apply Rubin's rule to combine analysis results:

```
proc sort data= LSMEstimates_imp;
  by trt01pn _imputation_;
run;

proc mianalyze data= LSMEstimates_imp;
  modeleffects estimate;
  stderr stderr;

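### The sample SAS code for the Cox hazard ratio and for the Week 16-24 FEV1 contrast needs opposite level orders of trt01pn, so under one coding one of the two carries the wrong direction under its label

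*SAP*

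**What the plan says.** **Cox model (SAP 2.4.4.2.3).** The sample PHREG code declares "class trt01pn eosbgpln cntygr1 nscopd csmoker ppredFev1/ param = glm". It then requests an exponentiated contrast, labelled SAR440340 versus placebo, with coefficients "trt01pn -1 1 / exp".

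**Key secondary FEV1 (SAP 2.4.4.2.1).** The text states the target: "Model-based average across Weeks 16, 20 and 24 will be compared between the treatment groups". The sample MIXED code declares "class usubjid sex csmoker trt01pn cntygr1 eosbgpln avisitn". The contrast runs over two lines: "lsmestimate trt01pn*avisitn 'Tx wks 16-24 avg minus pbo wks 16-24 avg' 0 0", then "1 1 1 0 0 -1 -1 -1/ divisor=3".

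**Imputed FEV1 data (SAP Appendix J, pattern mixture step 3).** The same contrast appears with the same signs: "1 1 1 0 0 -1 -1 -1 / divisor=3".

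None of these statements has an ORDER=, REF= or DESCENDING option, and neither document says which arm takes the lower value of trt01pn. The prose is consistent: every comparison is meant to be SAR440340 against placebo.

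**The concern.** Both procedures apply contrast coefficients by position, so a label is true only if the levels sort in the order the author had in mind. The Cox statement presumes one order and the FEV1 statement the other, for the same variable. If both are copied into production programs, one label is false.

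Depending on the coding, the affected result is one of these:

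- the Week 16-24 average contrast for pre-bronchodilator FEV1, its multiple-imputation analyses, and FVC if the code is reused (SAP 2.4.4.3.1 calls for a similar model);
- the hazard ratio for time to first AECOPD, and for the expanded AECOPD and CID endpoints if the code is reused (SAP 2.4.4.3.3 calls for the same approach).

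In the imputation analyses the final step pools only an estimate and a standard error, so nothing at that step would show a wrong sign.

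**Working it through.** No stated figure in the plan is at issue. The check sets the two coefficient vectors against the level order each one needs.

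**Assumptions.** Levels take the default sort order, which is the same in both input datasets. Within trt01pn*avisitn, visits vary fastest because trt01pn precedes avisitn in the CLASS list. Missing trailing coefficients count as zero.

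**Step 1, Cox.** Let β1 and β2 be the log hazards for the first and second levels. The statement gives

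exp(−1·β1 + 1·β2) = exp(β2 − β1), the second level relative to the first.

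The label requires SAR440340 relative to placebo, so placebo must be first and SAR440340 second.

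**Step 2, FEV1.** The full vector is 0 0 1 1 1 0 0 −1 −1 −1 with divisor 3. Read as five visits per arm, as its author evidently intended, it gives

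(mean of three visits, first level) − (mean of three visits, second level).

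The label requires treatment minus placebo, so SAR440340 must be first and placebo second.

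**Step 3, both codings.**

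| Order of trt01pn | Cox contrast | FEV1 contrast |
|---|---|---|
| Placebo first | SAR440340 / placebo, label true | placebo − SAR440340, reversed |
| SAR440340 first | placebo / SAR440340, inverted | SAR440340 − placebo, label true |

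No single order makes both labels true.

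**Step 4, effect on the printed result.** A hazard ratio θ with interval (L, U) would print as 1/θ with (1/U, 1/L). The SAP assumes no hazard ratio. For illustration only, treat its rate reductions in section 1.3 as hazard reductions:

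- 30% reduction: θ = 0.70, printed as 1/0.70 = 1.43
- 45% reduction: θ = 0.55, printed as 1/0.55 = 1.82
- 50% reduction: θ = 0.50, printed as 1/0.50 = 2.00

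An FEV1 difference d with interval (L, U) would print as −d with (−U, −L).

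**Step 5, why the FEV1 size cannot be stated yet.** Pre-bronchodilator spirometry is scheduled at seven post-baseline visits to Week 24: Weeks 2, 4, 8, 12, 16, 20 and 24 (protocol 1.3.1; SAP Table 6). That makes 2 × 7 = 14 cells against 10 coefficients. Laid over those cells, the vector compares the first level at Weeks 8, 12 and 16 with the second level at Weeks 2, 4 and 8. The sign conflict remains, because the positive coefficients still fall on the first level and the negative ones on the second. The quantity, however, is no longer the Week 16-24 average. With 14 visits per arm (data to Week 52), all ten coefficients fall within the first level and the contrast is not a treatment comparison at all.

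**The case against.** The strongest reply is that this is expressly sample code and the prose leaves no doubt about direction. A programmer who knows the coding would put it right, and must rewrite the FEV1 vector anyway because of its length. This stands as a limit on seriousness: the estimand is clear, and the defect is a correctable coding inconsistency.

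Planned outputs would also help to expose an error. The SAP asks for LS means by group, Kaplan-Meier probabilities by group and a log-rank p-value, and the by-visit LSMEANS differences identify the levels compared. A reversed contrast would disagree with these. Reversing the sign of a contrast leaves its two-sided p-value unchanged.

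A reader might infer three stronger things that the documents do not support.

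- **That a whole endpoint family would be reversed.** The FEV1 statement serves only Week 16-24 averages. Post-bronchodilator FEV1 at Week 24 has no Week 16 or 20 value and cannot reuse it.
- **That the planned 0.12 L benefit would print as −0.12 L.** Step 5 shows that the vector as written does not estimate that average.
- **That the primary analysis is caught too.** The GLIMMIX code in SAP 2.4.4.1 contains no labelled contrast, so it has no label to contradict.

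Appendix J also hints at which statement is wrong. Its control-based imputation of AECOPD counts multiplies txval by zero to obtain the control rate, so placebo appears to be the lower code there. If trt01pn follows the same order, the Cox line is right and the FEV1 signs are wrong. But txval is a different variable, so this is not proof.

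What the reply does not remove is the contradiction itself: nothing in the SAP tells a programmer which statement to trust.

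**Conclusion.** The conflict is real and should be corrected. Under a single coding of trt01pn, with no order or reference option, either the Week 16-24 average contrast or the Cox hazard ratio carries the wrong direction under its label.

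The consequence is confined to the sign or inversion of that estimate and its confidence interval. For a hazard ratio it is exact reciprocation; for FEV1 no figure can be given while the vector length is wrong. Significance statements based on two-sided p-values would not change on this account.

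The conclusion rests on the same level order in both input datasets and on the code being used as printed. The documents show nothing to the contrary on level order, but because the code is illustrative, an actual error in reported results is a risk and not a certainty.

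**What to change.** State the coding of trt01pn once in SAP 2.4.4, then align the statements in 2.4.4.2.1, 2.4.4.2.3 and Appendix J with it. Correct the length of the FEV1 vector in the same edit. For a dataset holding the seven post-baseline visits to Week 24, with divisor 3:

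- **Placebo first:** keep `-1 1` in the Cox statement and use `0 0 0 0 -1 -1 -1 0 0 0 0 1 1 1` for FEV1.
- **SAR440340 first:** change the Cox coefficients to `1 -1` and use `0 0 0 0 1 1 1 0 0 0 0 -1 -1 -1` for FEV1.

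As an optional safeguard, name placebo as the explicit reference in every model, and recheck positional coefficients afterwards in case that changes the level order. The cost is a few lines of SAP code, with no new data and no change to any endpoint, model or population.
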